5.1.1 COVID-19 Symptom Diary

Patients complete the COVID-19 Symptom Diary up to three times on Day 1, twice per day on Days 2–14 and once per day on Days 15–29. Expectation for assessments is as follows:

- Day 1, up to two of the following:
 - Prior to first dose assessment
 - Bedtime assessment
- Days 2–14:
 - Morning assessment
 - Bedtime assessment
- Days 15–29:
 - Bedtime assessment

Data will be analyzed as it was captured per the expected assessments above; time windows will not be implemented.

Missing data for individual symptoms at an assessment where data for other symptoms from the COVID-19 Symptom Diary are present will be set to the highest score on the Likert scale.

Missing data due to a missing assessment (i.e., all symptoms missing) where the assessment would be the first expected assessment to show efficacy criteria maintained for ≥ 21.5 hours (or ≥ 43 hours as appropriate) will be assumed to have met the efficacy criteria as long as the data at the next expected assessment following the missed assessment also has met the efficacy criteria.

5.2 PARTICIPANT DISPOSITION

Summaries of patient disposition, including the number and percentage of patients who are randomized, receive treatment, complete treatment, discontinue treatment, complete study, discontinue study, and the associated reasons for discontinuing treatment and study will be created. Summaries of study duration (in days) defined as the date of the study completion/discontinuation minus the date of first study treatment plus one, and visit disposition will also be created. Patient disposition summaries will be created using the efficacy-evaluable and the All Patients set, and will be tabulated by treatment group separately as well as combined.

5.3 PRIMARY ENDPOINT(S) ANALYSIS

The primary efficacy objective of this study is to evaluate the efficacy of RO7496998 (AT-527) compared with placebo in adult and adolescent patients and will be assessed based on the following endpoint:

- The time to alleviation or improvement of COVID-19 symptoms (Items 1–12 of the COVID-19 Symptom Diary) maintained for a duration of 21.5 hours (24 hours minus 10%, to allow some flexibility in the timing of assessments), defined as follows:
 - For new symptoms: time from randomization to the alleviation of COVID-19 symptoms (i.e., a score of 0 [none] or 1 [mild] on the COVID-19 Symptom Diary)
 - For pre-existing symptoms: time from randomization to when a patient's symptoms have been maintained or improved (note improved requires at least a single category improvement from baseline on the COVID-19 Symptom Diary Likert scale)

The primary efficacy endpoint definition includes both alleviation of new COVID-19 symptoms and maintenance/improvement of pre-existing COVID-19 symptoms to allow for the possibility that some patients may have concurrent conditions with symptoms similar to those observed with COVID-19 (e.g., cough in a patient with chronic obstructive pulmonary disease). At screening, patients will be assessed with a 14-item COVID-19 symptom severity assessment to identify pre-existing symptoms (within the prior 30 days), and assess if they worsened due to COVID-19. Symptoms that are not pre-existing are considered to be new symptoms and need to achieve sustained alleviation (score of 0 or 1) to meet the endpoint.

If a symptom is pre-existing, the patient is asked if the severity at screening is worse than what was experienced within the last 30 days prior to COVID-19:

- If the severity is not worse, the symptom must be maintained (no worsening) or improved to meet the endpoint.
- If the severity is worse, then a sustained improvement of at least one grade must be achieved to meet the endpoint. For example, a symptom classed as severe at screening must improve to moderate, mild, or none, and a symptom classed as moderate at screening must improve to mild or none.

The hazard ratio for TTAIS for RO7496998 (AT-527) and placebo arms will be tested using the stratified log-rank test with three regions (i.e., North America, Europe, and ROW) and high-risk factor (yes, no) included as the stratification factors. Kaplan-Meier plots, median time to response, 97.5% CIs, and p-values will be presented.

The log-rank test is most powerful when the assumption of proportional hazards holds. The proportional hazards assumption will be tested graphically using the log-cumulative hazard plot by treatment group. Should the proportional hazards assumption not hold, the Gehan-Wilcoxon test will be used to analyze the data.

The primary estimand is defined in [Table 2](#). The primary efficacy analysis population will be the efficacy-evaluable set, which consists of all patients who were randomized to treatment, received a dose of study treatment, and were RT-qPCR positive for SARS-CoV-2 at any point during the study.

5.3.1 Definition of Primary Endpoint

The time to alleviation or improvement of COVID-19 symptoms is defined as the time from randomization to the first time at which all COVID-19 symptoms from Items 1-12 of the COVID-19 Symptom Diary were either alleviated, maintained or improved for a minimum duration of 21.5 hours (24 hours minus 10%, to allow some flexibility in the timing of assessments). Alleviation, maintenance, or improvement of symptoms is defined as the time when all 12 COVID-19 symptoms from Items 1-12 of the COVID-19 Symptom Diary have been assessed by the patient as follows:

- For pre-existing symptoms (i.e., symptoms that existed prior to developing COVID-19) judged by the patient to be worse at screening:
 - Improvement of at least one grade on the Likert scale from baseline if the severity at baseline is graded moderate or severe:
 - Severe to moderate, mild, or none
 - Moderate to mild or none
 - Mild to mild or none
 - None to mild or none

Note: At screening, patients will only be asked if preexisting symptoms existed (within the last 30 days) and if they were worsened by COVID-19. Patients will be asked to rate the severity at baseline that needs to improve. To avoid recall bias, patients will not be asked to rate the severity of preexisting symptoms prior to COVID-19.

- For pre-existing symptoms (i.e., symptoms that existed prior to developing COVID-19) judged by the patient NOT to be worse at screening:
 - Maintained (no worsening) baseline severity if the severity at baseline is graded moderate or severe:
 - Severe to severe, moderate, mild, or none
 - Moderate to moderate, mild or none
 - Mild to mild or none
 - None to mild or none
- For new symptoms (i.e., symptoms that develop due to COVID-19 which present prior to or post baseline):
 - Alleviation of COVID-19 symptoms (i.e., a score of 0 [none] or 1 [mild] on the COVID-19 Symptom Diary):
 - Severe to mild, or none
 - Moderate to mild, or none
 - Mild to mild or none
 - None to mild or none

Where the baseline assessment for COVID-19 symptom severity is missing, the COVID-19 symptoms for a patient will be treated as new symptoms and therefore must meet the alleviation criteria even if symptoms had been identified as existing prior to developing COVID-19.

The primary endpoint will be tested using a two-sided significance level of 0.025.

5.3.2 Main Analytical Approach for Primary Endpoint(s)

The hazard ratio (HR) for TTAIS for RO7496998 (AT-527) and placebo arms will be tested using the stratified log-rank test with the following stratification factors: Region (North America, Europe, and ROW) and high-risk factor (yes, no), unless otherwise required as detailed in Section 5.1. Kaplan-Meier plots, median time to response with 97.5% CIs as estimated from the Kaplan-Meier curve, and difference in median time between treatment groups with 97.5% CIs using bootstrap method will be presented. In addition, the treatment groups will be compared descriptively using a Cox proportional hazards model adjusting for the stratification factors and a hazard ratio with a 97.5% CI will be produced.

The log-rank test is most powerful when the assumption of proportional hazards holds. The proportional hazards assumption will be tested graphically using the log-cumulative hazard plot by treatment group, where the plots for each treatment group will be parallel if the proportional hazard assumption holds. Should the proportional hazards assumption not hold, the Gehan-Wilcoxon test stratified by Region and high-risk factor will be used to analyze the data.

The primary estimand is defined in [Table 2](#). Summaries of the proportion of patients experiencing an intercurrent event and the time to the intercurrent event will be created. The WHO Drug Global B3 Format dictionary will be used for concomitant medications including rescue medication.

The statistical hypotheses for the primary endpoint is defined in Section [2.1](#).

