3.3.2 Rationale for Patient Population

The safety and efficacy of RO7496998 (AT-527) in hospitalized adult patients with moderate COVID-19 who have risk factors for poor outcome is currently being investigated in a Phase II study (AT-03A-001). Given the significant unmet need and disease burden in those with mild to moderate disease in the outpatient setting, this Phase III study is designed to further evaluate the efficacy and safety of RO7496998 (AT-527) in this population. Using the FDA guidance for industry (FDA 2020a), mild and moderate COVID-19 baseline severity categorization is defined as follows:

- Mild COVID-19
 - Positive testing by standard reverse-transcriptase polymerase chain reaction (RT-PCR) assay or equivalent test
 - Symptoms of mild illness with COVID-19 that could include fever, cough, sore throat, malaise, headache, muscle pain, gastrointestinal symptoms, without shortness of breath or dyspnea
 - No clinical signs indicative of Moderate, Severe, or Critical Severity
- Moderate COVID-19
 - Positive testing by standard RT-PCR assay or equivalent testing
 - Symptoms of moderate illness with COVID-19, which could include any symptom of mild illness or shortness of breath with exertion
 - Clinical signs suggestive of moderate illness with COVID-19, such as respiratory rate ≥ 20 breaths per minute, $\text{SpO}_2 > 93\%$ on room air at sea level, heart rate ≥ 90 beats per minute
 - No clinical signs indicative of Severe or Critical Illness Severity

In this study, *otherwise* healthy adult and adolescent patients without risk factors, as well as adult and adolescent patients with risk factors for hospitalization, will be enrolled. Randomization will be stratified based on the presence of one or more risk factors for severe COVID-19 as well as geographic region. Although the inclusion of a risk factor increases the individual risk of hospitalization, the course and progression of disease in those with mild to moderate disease alone should be similar irrespective of the presence or absence of a risk factor or the specific underlying risk factor.

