3. SAMPLE SIZE DETERMINATION

The required sample size of the efficacy-evaluable set is 1248 patients. It is assumed that the reverse-transcriptase quantitative polymerase chain reaction (RT-qPCR) positive rate for SARS-CoV-2 will be 90%. Therefore, approximately 1386 patients will be randomized to ensure an adequate number of patients in the efficacy-evaluable set. The total number of randomized patients may change based on the percentage of patients who are RT-qPCR positive during the study.

Rationale for the Target Sample Size

The required sample size has been calculated to ensure at least 90% power to detect a hazard ratio of 1.25 in the TTAIS of COVID-19 between the RO7496998 (AT-527) group and the placebo group. This corresponds to a 2-day improvement in the median TTAIS, assuming a median in the placebo group of 10 days ([Regeneron 2020](#)). Patients will be randomized to a 2:1 ratio to RO7496998 (AT-527) or placebo, respectively, and the fixed follow-up period will be 29 days. The study will require 1248 patients in the efficacy-evaluable set based on an expected 90% event rate (1122 events required) in order for the log-rank test to have at least 90% power with a two-sided significance level of 0.025, under the assumption of an exponential distribution. Additional patients may be enrolled

AT-527—F. Hoffmann-La Roche Ltd. and Atea Pharmaceuticals, Inc.

Statistical Analysis Plan CV43043

in order to observe 1122 events, where an event is meeting the primary endpoint. The minimal detectable difference is a hazard ratio of approximately 1.15, which equates to a difference in medians of approximately 1.33 days under the assumption of a 10-day placebo response.

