5.7.2.2 Baseline Disease Characteristics

- SARS-CoV-2 RT-PCR Status at Baseline
- Baseline viral load
- Seropositive status at baseline
- Presence of a high-risk factor
- Presence of individual high-risk factors
- Time from symptom onset to study treatment in days
- Number of symptoms present at baseline
- Number of symptoms from pre-existing conditions at baseline
- Number of symptoms with score ≥ 2 present at baseline
- Vaccinated for COVID-19
- Baseline systemic corticosteroid use
- Baseline inhaled corticosteroid use

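### Baseline symptom burden is collected but left out of the primary test; adding it is a cheap efficiency gain, not the repair of an error

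*SAP*

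**What the plan says.** - **Primary test.** Under SAP 5.3.2 the hazard ratio "will be tested using the stratified log-rank test with the following stratification factors: Region (North America, Europe, and ROW) and high-risk factor (yes, no". The fallback Gehan-Wilcoxon test uses the same two factors. So does the Cox model, which the SAP calls descriptive and which supplies the hazard ratio named as the summary measure in SAP Table 2.
- **Endpoint.** SAP 5.3.1 requires all 12 items to qualify together. A new symptom must reach mild or none. A pre-existing symptom that was worse at screening must fall one grade if moderate or severe. A pre-existing symptom that was not worse need only hold its baseline level.
- **What is collected.** SAP 5.7.2.2 lists "Number of symptoms present at baseline", the number scoring 2 or more, the number from pre-existing conditions, and days from onset to treatment. SAP 5.7.2 uses these to compare the groups. Onset time also defines one subgroup split in SAP 5.3.4.1. None of the sensitivity, supplementary or subgroup analyses adjusts for symptom burden or splits by it.
- **Risk factor.** Protocol 3.3.2 grants that a risk factor raises the chance of hospitalization, but says the course of mild to moderate disease "should be similar irrespective of the presence or absence of a risk factor or the specific underlying risk factor".
- **Elsewhere.** The ANCOVA in SAP 5.1 for continuous virology endpoints does adjust for the baseline value.

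**The concern.** Entry requires at least three symptoms of moderate intensity (Protocol 4.1.1), so patients may start with anything from 3 to 12 items at score 2 or 3. A patient with three new moderate items has much less to recover from than one with ten new severe items, yet both can sit in the same stratum. By the protocol's own reasoning, one of the two factors in use should say little about symptom course.

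When a prognostic baseline variable is left out of a log-rank comparison, the test is less sensitive than it could be with the same patients. The primary endpoint gates every key secondary endpoint (SAP 2.2), so sensitivity forgone here is forgone further down the hierarchy too.

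**Working it through.** **Step 1: the plan's own figure.** Inputs from SAP 3: "at least 90% power to detect a hazard ratio of 1.25 in the TTAIS of COVID-19"; "at least 90% power with a two-sided significance level of 0.025"; "randomized to a 2:1 ratio to RO7496998 (AT-527) or placebo"; "assuming a median in the placebo group of 10 days"; "the fixed follow-up period will be 29 days"; exponential times.

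Events = (z₀.₉₈₇₅ + z₀.₉₀)² / [p(1−p)(ln HR)²] = (2.241 + 1.282)² / [(2/3)(1/3)(0.2231)²] = 1121.7, so 1122, as stated. Power at 1122 events is 90.01%.

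Event rate by Day 29: placebo 1 − 2^(−29/10) = 0.866; active (median 10/1.25 = 8 days) 1 − 2^(−29/8) = 0.919; pooled (0.866 + 2 × 0.919)/3 = 0.901, against the stated 90%. Then 1122/0.90 = 1247 (stated 1248) and 1248/0.90 = 1387 (stated 1386). The plan's arithmetic stands.

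**Step 2: is burden likely to be prognostic?** Under SAP 5.3.1 the event occurs only when the slowest item qualifies, and each new item at score 2 or 3 adds a condition still to be met. A link with time to event is close to built in. Its strength is given nowhere, so it must be assumed.

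**Step 3: simulation.** 1248 patients (832:416), exponential times, placebo population median 10 days, censoring at Day 29, and six region-by-risk strata without effect on outcome. Burden x is standard normal and multiplies the recovery hazard by exp(−b·x), so b is the log-hazard SD. The hazard ratio is 1.25 at any given burden. The planned six-stratum log-rank test is compared, on the same data, with the same test with burden thirds added (18 strata). There were 3000 replicates per row.

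| b | Planned, % | Thirds added, % | Gain, points | Gain in repeat runs |
|---|---|---|---|---|
| 0 | 89.1 | 88.3 | −0.8 | −1.1; about +1 |
| 0.2 | 86.5 | 86.2 | −0.3 | +1.1; about 0 |
| 0.3 | 83.7 | 86.3 | +2.6 | +2.6; +2.3; about +4 |
| 0.5 | 75.8 | 84.8 | +9.0 | +8.0; about +8 |

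Simulation error is about 0.5 to 0.9 points per power figure. The +1 at b = 0 is noise, since an inert factor cannot help. A fair summary is −1 to 0, 0 to 1, 2 to 4 and 8 to 9 points.

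**Step 4: type I error.** Under no treatment effect with b = 0.5 (4000 replicates), rejection was 2.7% for the planned test and 2.5% with thirds, against a nominal 2.5%.

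**Step 5: what the table does not show.** The distance of the planned column from 90% is not a shortfall in the plan, for two reasons.
- SAP 3 ties 1.25 to medians of 10 and 8 days, which is a population-average effect. Simulated that way (2000 replicates), planned against thirds is 86.7% against 90.0% at b = 0.3, and 88.0% against 93.2% at b = 0.5. The gain remains, at 3.3 and 5.2 points, while most of the apparent shortfall goes.
- N is fixed at 1248, so events fall from 0.901 × 1248 = 1124 at b = 0 to 0.863 × 1248 = 1077 at b = 0.5. SAP 3 allows further enrolment to reach 1122 events.

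Only the difference between the two columns should be quoted.

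**The case against.** The strongest reply is that nothing here is wrong. Stratifying by the randomization factors is valid, the sample size reproduces, and type I error is held. Without a documented prognostic strength, the gain could be nil: a run at b = 0.1 gave 88.2% planned against 87.6% with thirds. All of this stands, and it is why the point is an improvement and not a correction.

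Four stronger readings are tempting, and the documents do not support them.
- **The trial is underpowered.** Step 5 shows why this does not follow.
- **The planned hazard ratio is biased towards 1.** A hazard ratio unadjusted for burden is a different quantity, averaged over burden. It is biased only if the conditional one is the target, and Table 2 does not say which is meant.
- **Chance imbalance in burden passes unchecked into the result.** The standard error of the group difference is √(1/832 + 1/416) = 0.060 SD. A 1.96-SE imbalance is therefore 0.118 SD, which shifts the hazard ratio by a factor of 1.024 at b = 0.2, 1.036 at b = 0.3 and 1.06 at b = 0.5. The test's error rate already allows for this.
- **The high-risk factor does not belong in the test.** It is a randomization factor, and keeping it is proper whatever its prognostic value.

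It is also fair to object that a plain count of items scoring 2 or more fits the endpoint poorly. It would count a pre-existing symptom that already meets its target. The diary baseline may be missing (SAP 5.3.1) or taken up to 4 hours after the first dose (SAP 5.1). These objections shape the fix; they do not remove the gain.

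**Conclusion.** The point holds as a low-cost improvement. The planned analysis is valid and adequately sized on its own assumptions, but it sets aside a baseline measure that the trial collects and that very likely predicts the outcome. The possible gain is large compared with the possible loss: at worst about 1 power point, little or nothing at SD 0.2, and worthwhile from about SD 0.3. The size rests on the assumed prognostic strength, a hazard ratio of 1.25 at given burden, N fixed at 1248, and a single normally distributed burden score cut into thirds. The direction rests only on burden being related to recovery time, which the endpoint's construction makes very likely.

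**What to change.** Before unblinding, amend the SAP as follows.

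1. In 5.3.2, add one baseline burden factor, in pre-set thirds, to the stratified log-rank test and to the fallback Gehan-Wilcoxon test. Define burden as the number of Items 1–12 that do not already meet their SAP 5.3.1 target at baseline, so that pre-existing symptoms not worse at screening are left out.
2. Use the screening severity assessment (Protocol Appendix 1) where the diary baseline is missing, and state which source applies when the only diary entry follows the first dose. Combine sparse strata as SAP 5.1 allows.
3. In the descriptive Cox model, add the burden score and days since symptom onset as covariates. State in Table 2 that this hazard ratio is conditional on them.
4. Keep the two-factor log-rank test as a sensitivity analysis.
5. SAP 5.1 carries the 5.3.2 methods over to the time-to-event secondary endpoints, so say whether the new factor applies there. Record the change in SAP Appendix 1, since Protocol 6.4.1 names only two factors.

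Cost: wording only, on data already collected. The downsides are up to 18 strata in place of 6, about 1 power point if burden turns out not to be prognostic, and a hazard ratio to be read as conditional.

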5.3.3 Sensitivity Analyses for Primary Endpoint(s)

To support the primary analyses, the following sensitivity analyses will be conducted:

- To test the sensitivity of the results to the special case of handling missing data, all missed assessments will be assumed not to have met the efficacy criteria.
- To test the sensitivity of the results to the COVID-19 symptoms followed, only baseline presenting symptoms are required to meet the relevant criteria.
- To test the sensitivity of the results to the statistical test performed, the stratified Gehan-Wilcoxon test will be used.
- To test the sensitivity of the results to adjustment by the stratification factors, an unstratified log-rank test will be performed.

5.3.4 Supplementary Analyses for Primary Endpoint(s)

5.3.4.1 Subgroup Analyses for Primary Endpoint(s)

The generalizability of primary endpoint results when comparing RO7496998 (AT-527) to placebo will be investigated by estimating the treatment effect in subgroups.

Summaries of primary endpoint by the following subgroups will be provided:

- Stratification factors:
 - Region (North America, Europe, and ROW)
 - Presence of a high risk factor for hospitalization due to COVID-19 (yes, no)
- Key baseline demographics:
 - Age (Adolescent 12–<18 years, Adult <65 years, Adult \geq 65 years)
 - Sex (Female, Male)
 - Race/Ethnicity
- Disease characteristics:
 - Time from symptom onset to study treatment in days (\leq 3, $>$ 3)
 - Vaccinated for COVID-19 (Yes, No)

- Baseline viral load (high, low; based on median baseline viral load)
- Seropositive status at baseline (Yes, No)
- Presence of a high-risk factor: Obesity (Yes, No)
- Presence of a high-risk factor: Cardiovascular disease (Yes, No)
- Presence of a high-risk factor: Chronic lung disease (Yes, No)
- Presence of a high-risk factor: Chronic metabolic disease (Yes, No)
- Presence of a high-risk factor: Immunocompromised (Yes, No)
- Presence of a high-risk factor: Chronic liver disease (Yes, No)
- Presence of a high-risk factor: Chronic kidney disease (Yes, No)

